## 2.0 SPECIFIC AIMS

To investigate our hypothesis, we will randomize fatigued ovarian cancer survivors into 6 weeks of daily: 1. Relaxing self-acupressure (n=57); 2. Sham self-acupressure (n=57); or 3. No treatment (n=57) followed by 18 weeks of no acupressure and investigate the following aims:

1. Examine the effect of 6 weeks of daily self-administered relaxing acupressure compared to self-administered sham acupressure or no treatment on:

- A. Persistent fatigue (**Primary aim**) -- measured with The Brief Fatigue Inventory;
- B. Quality of life (**Secondary aim**) -- using the Functional Assessment of Chronic Illness Therapy Measurement System, specifically the ovarian cancer specific instrument;
- C. Sleep Quality (**Secondary aim**) -- using the Pittsburgh Sleep Quality Index;
- D. Symptoms commonly associated with persistent fatigue (**Exploratory aim**) (sleep disturbance, pain, cognitive function, mood, and female sexual function) -- using Patient Reported Outcomes Measurement Information System.

**2 (Exploratory aim).** To investigate the duration of effect self-administered relaxing acupressure as compared to self-administered sham acupressure or no treatment during the 18 weeks following the end of acupressure treatment (carry-over phase) on persistent fatigue, quality of life, sleep quality, and symptoms commonly associated with persistent fatigue (sleep disturbance, pain, cognitive function, mood, and female sexual function) using the measurement tools described for the primary aim.

Both acupressure treatments will be delivered via the MeTime Acupressure app in association with the AcuWand.

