**Table 2**

	Screening phone call	Baseline Week 0	Treatment Phase Weeks 1 - 6	Follow-up Week 6 (- 2 days/+5 days)	Follow-up Week 12 (- 2 days/+5 days)	Follow-up Week 24 (- 2 days/+5 days)
Phone Screen	X					
Screening Survey	X					
BFI	X	X		X	X	X
PHQ-2	X					
Consent	X					
Pt. Info & Dem.	X					
Concomitant of Medications		X				
Diagnosis & Treatment of initial cancer		X				
FACT-O		X		X	X	X
PSQI		X		X	X	X
PROMIS		X		X	X	X
IPAQ		X				
SCQ		X				
FSQ		X				
MAIA		X		X		
Daily Logbook			X			
Acupressure Fidelity				X		
Assessment of blinding				X		
AcuWand Comfort				X		
Final Evaluation						X

**Administering Study Assessments.** All potential participants will be screened over the phone using a brief questionnaire to confirm eligibility for the study. Enrolled participants will then receive an email link to their RedCAP study measures at baseline, weeks 0, 6, 12 and 24. All the surveys will be administered at all-time points with the exception of descriptive and baseline assessments, which will only be collected at week 0; fidelity, blinding and adherence, which will only be asked at week 6; and a final evaluative questionnaire about the participants' perception of the study and the use of the AcuWand device. Adverse events will be collected at all-time points. Inspirational reminder emails, texts, or phone calls (as appropriate for a given participant) will be made to encourage the highest possible response rate to each round of study assessments. Participants without an email account will be assisted in obtaining a free Gmail account and how to access it on their computer tablet by study staff. Those participants who do not have access to Wi-Fi will be assisted in finding free Wi-Fi in their community (e.g., public library, Starbucks, McDonalds, etc.) IT study staff will be available to assist participants with any questions that may arise. E-mail is required so that study instruments may be accessed through surveys in RedCAP.

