### Statistics Section.

The primary aim of this study is to investigate the differential effects of different modes of acupressure (relaxing vs. sham vs. no treatment) on fatigue as measured by the BFI in ovarian cancer survivors at week 6. The BFI, which measures the average degree of fatigue, gives a score that ranges between 0 and 10, with higher numbers indicating more fatigue. To investigate the difference in BFI between the three study arms, we shall use linear mixed-effects regression analysis with BFI as outcome, *week* as the within-subjects factor with four levels (0, 6, 12, 24) and *group* (relaxing acupressure, sham acupressure, no treatment) as the primary between-subjects factor. Of interest is the group-by-week interaction (to be included in the model), significance of which will indicate differences in extent of decrease between the arms. The covariate cancer stage at diagnosis and the interaction term group-by-stage will be added to models. Post-hoc sliced main effect of weeks within each study arm will be estimated. A *subject* random-effect will be used to account for the clustering effect within the four measurements on the same subject. Model diagnostics will be carried out to confirm the distributional assumptions and appropriate corrective actions (e.g. transformation) will be performed as needed. Models with more flexible covariance pattern (e.g. unstructured covariance, heterogeneity across groups) will be explored. An additional analysis with a spline version of weeks will be carried out which uses *week* as a continuous variable allowing one to estimate the rate of change in BFI.

A secondary analysis with BFI will also be carried out which investigates the difference in proportion of fatigued subjects ( $BFI \geq 4$ ) across the three study arms. The analytical framework will be that of a mixed-effects logistic regression model with presence of fatigue ( $BFI \geq 4$  yes/no) being the dichotomous outcome. Apart from group, week, and group-by-week interaction as primary covariates, the model will also be adjusted for baseline status of severity. Remaining covariates in the model are identical to those in the continuous BFI model. The clustering effect due to subject will be accounted for using a generalized estimating equations approach under a generalized linear mixed models framework.

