To investigate the duration of effect of self-administered relaxing acupressure as compared to self-administered sham acupressure or no treatment during the 18 weeks following the end of acupressure treatment (carry-over phase) on persistent fatigue, quality of life, sleep quality, and symptoms commonly associated with persistent fatigue (sleep disturbance, pain, cognitive function, mood, and female sexual function) we will break up the observation period into two phases. In the first phase BFI and other study measures will be obtained by averaging week 0-week 6 measures and will indicate the status until end of the acupressure treatment (treatment-phase). The second phase comprises of week 7-week 24 and indicates the washout phase (washout). To investigate the difference in BFI and other study measures between the three study arms, we shall use mixed- effects regression analysis with average BFI and other study measures in the two phases as outcome, phase as the within-subjects factor and group (RA, SA, standard of care) as the primary between-subjects factor. We shall carry out an analysis with the phase variables as treatment-phase and washout as the levels. The purpose of investigating the model will compare the differences between the treatment and washout period across groups (phase-group interaction).

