## 9.0 STATISTICAL METHODS

**Power Analysis.** Our power analysis is based on our primary aim to, “Examine the effect of 6 weeks of daily self-administered relaxing acupressure compared to self-administered sham acupressure or no treatment on persistent fatigue as measured with The Brief Fatigue Inventory.” Although we will run a larger model for the analysis, in the power calculation we focus on the specific components of the model in which we are interested. Towards that end, we compute the power via simulation using a mixed effects model with a between-subject factor group (3 levels), a within-subject factor week (0, 6, 12, and 24), group-by-time interaction and a random subject effect. The mean BFI at baseline is assumed to be 5.5, whereas values at end of treatment were assumed to be 4.5, 3.5, and 2, respectively for no treatment, sham acupressure and relaxing acupressure arms. The between-subject variance is assumed to be 4 at all time-points whereas the variance of the random subject component is taken to be 4 also (yielding an intra-class correlation of 0.5). These assumed values are estimates based on our pilot data. For this configuration, the power for detecting a significant week-by-group interaction is greater than 95% with a sample size of 50 evaluable participants per treatment arm (we anticipate a ~13 % drop out with the goal of 150 completers for a total sample size of 171) and a 5% level of significance. Such a model is able to detect a post-hoc difference between the relaxing acupressure and each of the other two arms with more than 90% power at a reduced 0.01 level of significance in order to protect against Type I error probability inflation. In the second phase after the treatment period, it is anticipated that both the no-treatment and the sham acupressure arms will experience a bounce

back close to the baseline level, while the relaxing acupressure arm will maintain its end-of-treatment average. Thus, the differences will be more pronounced than those in the active treatment phase, and we will be well

powered to detect the effect size.

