**Table 3: Mean and standard deviation of changes between baseline and 6 weeks by study arm**

	N	Mean	Std. Deviation
True Acupressure	41	-1.9621	2.04466
Sham Acupressure	45	-1.2988	1.63485
Usual Care	51	-0.4336	1.51849
Total	137	-1.1752	1.82757

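### The carry-over analysis averages pre-treatment week 0 into the treatment phase, so a zero phase-by-group interaction corresponds to losing half the effect, not to keeping it

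*Combined protocol and SAP*

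**What the plan says.** Aim 2 in section 2.0, labelled exploratory, is "To investigate the duration of effect self-administered relaxing acupressure as compared to self-administered sham acupressure or no treatment" over the 18 weeks after treatment ends. It covers fatigue, quality of life, sleep and associated symptoms.

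The Exploratory Aims part of the Statistics Section splits follow-up into two phases:

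- Treatment phase: "In the first phase BFI and other study measures will be obtained by averaging week 0-week 6 measures".
- Washout: "The second phase comprises of week 7-week 24 and indicates the washout phase (washout".

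A mixed model is then fitted to the phase averages, with phase as the within-subjects factor and group as the between-subjects factor. Its stated purpose is that it "will compare the differences between the treatment and washout period across groups (phase-group interaction". No baseline adjustment is given, and no rule for reading the interaction.

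Section 4.1 has participants complete "RedCAP study measures at baseline, weeks 0, 6, 12 and 24". Table 2 shows no other assessment of the outcomes that this aim uses.

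The primary model in the same section takes week "as the within-subjects factor with four levels (0, 6, 12, 24", with a group-by-week interaction. It therefore keeps weeks 0 and 6 apart, but it names no between-arm contrast of week 12 or 24 against week 6.

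**The concern.** Aim 2 asks whether an effect reached at the end of treatment lasts. The natural reference is week 6. The planned reference is an average in which half the weight falls on a measurement taken before treatment began, when randomised arms are expected not to differ. The treatment-phase difference between arms is therefore half the true end-of-treatment difference, and the interaction compares washout with that halved figure.

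An effect that lasts in full then looks as if it grew after treatment stopped, and an effect that halves looks unchanged. The same construction applies to every outcome under Aim 2, and nothing in the plan tells a reader where the zero of this interaction lies.

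**Working it through.** **Inputs**

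- Assessment weeks 0, 6, 12 and 24 (section 4.1, Table 2). The treatment-phase value is (week 0 + week 6)/2 and the washout value is (week 12 + week 24)/2.
- Baseline mean BFI 5.5 in all arms; "values at end of treatment were assumed to be 4.5, 3.5, and 2, respectively for no treatment, sham acupressure and relaxing acupressure arms" (section 9.0). The week-6 effects D of relaxing acupressure are 2 − 4.5 = −2.5 against no treatment and 2 − 3.5 = −1.5 against sham.
- 50 evaluable women per arm; 5% level overall and 1% for pairwise comparisons (section 9.0).
- Residual variance ve. Section 9.0 gives two variances of 4 and an intra-class correlation of 0.5. Read as subject 4 plus residual 4, ve = 4. Read as total variance 4, ve = 2. Results are for ve = 4, with ve = 2 in brackets.
- Complete data and a random-intercept model.

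**The plan's own figure.** Section 9.0 states more than 95% power for the week-by-group interaction; it states none for the phase-by-group interaction. Changes from week 0 to week 6 are −1, −2 and −3.5, with sum of squared deviations 3.167 and variance 2ve = 8. The noncentrality is 50 × 3.167/8 = 19.79, and F(2,147) gives 98.2%. All four time points give over 99%. The stated figure is reproduced.

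**What the interaction estimates.** Let D be the between-arm effect at week 6 and r the fraction retained, averaged over weeks 12 and 24.

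- Planned: rD − (0 + D)/2 = (r − 0.5)D.
- Change since end of treatment: rD − D = (r − 1)D.

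The planned quantity is zero at r = 0.5. Full retention and complete loss give +0.5D and −0.5D, equal in size and opposite in sign.

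**Size of the interaction** (BFI points; relaxing minus comparator)

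| Course after week 6 | Comparator | Planned interaction | Change since week 6 |
|---|---|---|---|
| Fully sustained | no treatment | −1.25 | 0 |
| | sham | −0.75 | 0 |
| Half lost | no treatment | 0 | +1.25 |
| | sham | 0 | +0.75 |
| All lost | no treatment | +1.25 | +2.50 |
| | sham | +0.75 | +1.50 |
| Controls return to 5.5, relaxing stays at 2 | no treatment | −2.25 | −1.00 |
| | sham | −2.75 | −2.00 |

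The last scenario is the one section 9.0 anticipates. There the relaxing arm goes from (5.5 + 2)/2 = 3.75 to 2.0, an apparent fall of 1.75 although it does not change after week 6.

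**Rejection rates.** The subject effect cancels in the phase difference, whose variance is ve/2 + ve/2 = ve. For the mean of weeks 12 and 24 minus week 6 it is ve/2 + ve = 1.5ve.

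- *Fully sustained, planned 2-df test at 0.05.* Phase differences are −0.5 (no treatment), −1.0 (sham) and −1.75 (relaxing), with sum of squared deviations 0.792. The noncentrality is 50 × 0.792/4 = 9.90 (19.79), so the rate is 80% (98%). A test of change from week 6 would reject at its nominal 5%.
- *Fully sustained, pairwise.* SE = √(2ve/50) = 0.400 (0.283). Relaxing against no treatment: 87% (99%) at 0.05 and 69% (96%) at 0.01. Relaxing against sham: 46% (75%) at 0.05 and 23% (51%) at 0.01.
- *Half lost.* The planned 2-df test rejects 5% of the time. The week-6 contrast has noncentrality 50 × 0.792/(1.5 × 4) = 6.60 (13.19), which gives 62% (91%).

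Simulation agreed with these rates within 0.01.

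**Smaller effects, from Table 3** ("Mean and standard deviation of changes between baseline and 6 weeks by study arm"). The pooled variance of change is (40 × 2.04466² + 44 × 1.63485² + 50 × 1.51849²)/134 = 2.986, so SD = 1.73 and ve = 2.986/2 = 1.49. The week-6 effects are −1.53 against usual care and −0.66 against sham. If fully sustained, and with all 41, 45 and 51 women followed to week 24, the planned interactions are −0.76 and −0.33. The 2-df test is significant 76% of the time. Pairwise rates are 84% and 24% at 0.05, and 64% and 9% at 0.01.

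**The case against.** - **The plan never says that a null interaction will be read as maintenance.** Correct. The defect lies in the quantity estimated, not in a stated conclusion. The 50% refers to a true interaction of zero with arms balanced at baseline, and it is an average over weeks 12 and 24: full retention at week 12 and total loss at week 24 also gives zero. A non-significant result proves neither loss nor maintenance.
- **Other planned analyses help.** The primary model has week at four levels, within-arm effects of week and a spline, and analogous models are planned for the other outcomes. They show each arm's course after week 6, and the between-arm difference within the washout phase is not distorted. This limits the damage. None of it is a designated between-arm comparison of weeks 12 and 24 with week 6, and the phase interaction is the model named for duration.
- **The fully sustained scenario is not what section 9.0 expects.** It expects both control arms to rebound. The interaction then has the right direction and the widening is real, but it is overstated by 1.25 and 0.75 points. With the Table 3 effects the distortion against sham is only 0.33 points. Both points stand as limits on size.
- **The aim is exploratory.** It is, and this keeps the point below the primary analysis in priority. It does not make the contrast answer the question.

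**Conclusion.** The concern holds. The analysis designated for duration of effect measures washout against half the end-of-treatment effect, so its zero sits at 50% average retention. The halving follows from the assessment schedule and randomisation alone, given equal weight to weeks 0 and 6; a chance baseline imbalance would shift it.

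The rejection rates rest further on the week-6 means in section 9.0 or Table 3, a random-intercept model and complete data. Across the two readings of the variance and the Table 3 effects, the overall test would be significant in about 76% to 98% of trials in which nothing changed after week 6. It is a should-fix matter: the error is in the specification, but it is confined to the exploratory aim.

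**What to change.** Replace the phase averages with contrasts from the four-level week model, reported as estimates with confidence intervals:

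1. Between-arm differences at weeks 12 and 24 relative to baseline: is an effect present?
2. Between-arm differences in change from week 6 to week 12 and from week 6 to week 24: has it faded?

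If two phases are kept, take week 6 alone as the treatment-phase value, with week 0 as a covariate or a separate level. State that maintenance will be judged from the interval and not from a non-significant test.

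The cost is SAP wording only; the model and data are already planned. One caution: section 9.2 and Tables 3 and 4 report week-6 changes by arm, apparently from this trial. If so, the revised contrasts should be labelled as specified after those results were seen.

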## 3.0 METHODS

**Study Design.** We propose a randomized, controlled clinical trial comparing relaxing acupressure to sham acupressure and no treatment for persistent fatigue in ovarian cancer survivors. The study will be 25 weeks in

duration: **Phase I (screening phase;** 7 days in duration/weeks -1 to 0), consisting of telephone screen for study eligibility, obtaining informed consent, random assignment to treatment group, and shipment of computer tablet and AcuWand, if appropriate; **Phase II (active treatment phase;** 6 weeks in duration), which will consist of performing once daily self-acupressure—sham or relaxing—with the study app and the AcuWand or no treatment with outcomes including baseline and 6-week subjective measures of fatigue; sleep quality, pain, female sexual function, cognition, and quality of life; **Phase III (carry-over phase)** is an 18-week follow-up to evaluate fatigue, sleep quality, pain, female sexual function, cognition, and quality of life after completion of the acupressure treatments with outcomes assessed at 12 and 24 weeks. Our studies have indicated that the effects of self-acupressure can persist for 4 weeks after the end of treatment and acupuncture interventions in chronic pain populations have seen sustained effects ranging from 6 months to one-year post-intervention. As such, we intend to determine if acupressure has sustained impacts beyond 4 weeks after the end of treatment. **All groups including the no treatment group will have an equal number of study contacts.**

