## 4.0 Design Considerations.

**Justification for Sham Acupressure and No Treatment Arms.** We chose to add a sham acupressure arm to this study so that we had a control arm that could be blinded to participants and study staff. Sham acupressure also controls for placebo (non-specific) effects associated with acupressure, and thus will allow us to estimate the specific or true effects of the relaxing acupressure treatment. The no treatment arm controls for regression to the mean and is an accurate reflection of what the majority of cancer survivors are receiving for their persistent fatigue from health care providers—no treatment.

**Justification for Acupressure Dose (3 minutes per acupoints) and Duration (6 Weeks).** In our original

acupressure pilot study in adult cancer patients, we found that, regardless of treatment arm, the number of minutes performing acupressure was significantly correlated with reduction of fatigue or sleepiness. Participants (per their study logbooks) who stimulated their points for shorter periods of time, i.e., 1 minute, had less of an effect on fatigue and sleepiness compared to those who stimulated their points for 3 minutes. We also determined, from pilot work with fatigued cancer patients assigned to self-administered acupressure for 12 weeks, that change in fatigue improved over 6 weeks and then plateaued, with no further significant improvement. Finally, our preliminary data from our randomized controlled trial in fatigued breast cancer subjects demonstrated improvements in subjective fatigue outcomes at 6 weeks.

**Justification for 24-Week Follow-up.** Our pilot data in fatigued adult breast cancer patients demonstrates that our 6-week acupressure intervention has sustained effects on fatigue, sleep and quality of life outcomes up to 4 weeks after the cessation of the acupressure treatment. Other acupuncture interventions mainly in chronic pain populations have seen sustained effects ranging from 6 months to one year post-intervention and similarly, behavioral therapies for fatigue have sustained impacts of from 24 to 26 weeks (6 months). For acupressure to be a widely used and implemented treatment we would need to observe sustained effects on fatigue reduction of the intervention similar to other pain treatments. As such, we are proposing a 24-week post-treatment follow-up for this study.

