**Handling Missing Data.** The *linear mixed-effects* framework is an intent-to-treat framework in the sense that it uses all available data at all time-points. So if there are missing outcome values in any phase due to participant dropout, the usual analysis will still be valid. If the proportion of dropouts is substantial (20% or more) in either arm, then we shall also perform a weighted analysis with weights equal to the inverse of the probability of dropout. On the other hand, missing covariate values for the subject-level information will be imputed using multiple imputation methods. All missing values will be imputed using the chained equation method. The advantage of using this technique is its flexibility in allowing different types of variables (categorical and continuous) to be imputed together without requiring any multivariate joint distributional assumption. In this method, the missing values are sequentially updated using bootstrap or Markov Chain Monte Carlo based on multiple regression models with other variables as covariates. This procedure will be carried out for a number of repetitions or cycles, thereby constructing an ‘imputed’ dataset. Ten such ‘imputed’ datasets will be used for the final analysis, a number which is considered adequate for most applications. Finally, we shall combine the results from the ten regressions with the imputed data using Rubin’s formula.

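### The duration-of-effect analysis averages weeks 12 and 24 into one washout value, so the model assigned to Aim 2 cannot show how long the effect lasts; the week model already planned can

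*Combined protocol and SAP*

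**What the plan says.** Section 2.0 states exploratory Aim 2: "To investigate the duration of effect self-administered relaxing acupressure as compared to self-administered sham acupressure or no treatment during the 18 weeks" after treatment ends. Section 3.0 describes the carry-over phase as an 18-week follow-up "with outcomes assessed at 12 and 24 weeks", and Table 2 shows no other outcome visit after week 6. Section 3.0 also gives the purpose: "we intend to determine if acupressure has sustained impacts beyond 4 weeks after the end of treatment". Section 4.0 supports the long follow-up partly by noting that "behavioral therapies for fatigue have sustained impacts of from 24 to 26 weeks (6 months").

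The Statistics Section then describes the analysis for this aim. Each outcome is reduced to two values per woman. The treatment-phase value comes from "averaging week 0-week 6 measures". For the other value, "The second phase comprises of week 7-week 24 and indicates the washout phase (washout"). The mixed model takes these two averages as its outcome, and the comparison of interest is the phase-by-group interaction.

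The same section plans a different model for BFI: week as a four-level factor (0, 6, 12, 24), group, group-by-week, week effects sliced within each arm, and a spline version of week. Analogous models follow for FACT-O, PSQI and the PROMIS measures. The primary and secondary analyses are directed at week 6. No comparison between arms at week 12 or at week 24 is named for Aim 2.

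**The concern.** Duration is a question about time since the end of treatment. The trial observes that period twice, 6 weeks and 18 weeks after treatment stops. Averaging the two visits for each woman before modelling discards the order in which they occurred, and no later step in that model can recover it. This applies to every outcome under Aim 2.

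At stake is how the follow-up result is read. A result described as covering weeks 7 to 24 could come from an effect that had vanished by week 24, from a partial effect that persisted, or from something in between. The week-24 visit exists to tell these apart.

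**Working it through.** **Inputs.** From the Power Analysis in section 9.0: baseline BFI 5.5; week-6 means 4.5 (no treatment), 3.5 (sham) and 2 (relaxing); 50 evaluable women per arm; two variance components of 4 with intra-class correlation 0.5. I read these as subject variance 4 and residual variance 4. The other reading is a total variance of 4, with 2 and 2. Visits are at weeks 0, 6, 12 and 24.

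**The plan's own figure.** The power section claims more than 95% power for the week-by-group interaction at the 5% level. With weeks 0 and 6 only, the squared interaction effects sum to 1.583, so the noncentrality is 50 × 1.583 / 4 = 19.8 on 2 and 147 df, giving 98%. With four visits and week-6 means held, the noncentrality is 29.7 on 6 and 441 df, giving 99%. The claim reproduces, and it comes from the week model. The plan states no figure for the phase model.

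**Phase means in the relaxing arm.** Treatment phase = (week 0 + week 6)/2; washout = (week 12 + week 24)/2.

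- Full at week 12, gone at week 24 (5.5, 2, 2, 5.5): (5.5 + 2)/2 = 3.75 and (2 + 5.5)/2 = 3.75.
- Half kept at both (5.5, 2, 3.75, 3.75): (5.5 + 2)/2 = 3.75 and (3.75 + 3.75)/2 = 3.75.

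**General form.** Let D be the between-arm difference at week 6, and let fractions a and b of it remain at weeks 12 and 24. The treatment-phase difference is D/2, the washout difference is D(a + b)/2, and the interaction is D(a + b − 1)/2. Only the sum a + b enters. For relaxing minus sham, D = 2 − 3.5 = −1.5:

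| Course | a | b | Treatment phase | Washout | Interaction |
|---|---|---|---|---|---|
| Full, then gone | 1 | 0 | −0.75 | −0.75 | 0 |
| Half at both | 1/2 | 1/2 | −0.75 | −0.75 | 0 |
| None, then full | 0 | 1 | −0.75 | −0.75 | 0 |
| Linear decay to zero at week 24 | 2/3 | 0 | −0.75 | −0.50 | +0.25 |
| One third at both | 1/3 | 1/3 | −0.75 | −0.50 | +0.25 |

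Relaxing minus no treatment (D = −2.5) behaves the same way: the first three rows give −1.25, −1.25 and 0. In 4,000 simulated relaxing-versus-sham trials, the interaction was rejected at 5% in 4.9% of runs under each of the first two courses, which is the null rate.

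**The same courses with visits kept apart.** Relaxing minus sham is −1.50 then 0 for the first course, and −0.75 then −0.75 for the second. The SE of the between-arm difference in week-24-minus-week-12 change is √(2 × 4 × 2/50) = 0.566, or 0.40 with residual variance 2. Under full-then-gone, power at 5% for that contrast (noncentral t, 98 df) is about 75% or 96% against sham and at least 99% against no treatment. Under half-kept, power for the week-24 difference in change from baseline is lower: about 26% or 46% against sham (0.75 points) and 59% or 87% against no treatment (1.25 points).

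**Precision.** A single-visit difference has SE √(8 × 2/50) = 0.566. The two-visit average has SE √(6 × 2/50) = 0.490. The ratio is 1.15 under either variance reading.

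**The case against.** The strongest reply is that the needed model is already in the plan. Week is a four-level factor with group-by-week terms, so differences at weeks 12 and 24 can be estimated. The paragraph on the PROMIS outcomes applies it without limiting it to week 6. This stands. A reader might infer that Aim 2 cannot be answered at all, and the documents do not support that. What remains is that the plan sends the duration question to the phase model and names no week-12 or week-24 contrast between arms.

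Second, the stated purpose is an effect beyond 4 weeks after treatment, and both visits are later than that, so a washout average speaks to it in part. Also, the power section expects the relaxing arm to hold its gain and the other arms to return towards baseline. On that course little is lost by averaging. Both points are fair, but the analysis should not depend on the expected course being true.

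Third, a reader might infer that the plan is very likely to declare a lasting effect when none is left at week 24. If relaxing follows 5.5, 2, 2, 5.5 and the comparators are back at 5.5, the plain washout difference is 1.75 with SE 0.490, significant about 94% of the time. That is not the test named. The phase-by-group contrast is 0.5 against no treatment and 1.0 against sham, with SE √(4 × 2/50) = 0.40 and power of about 24% and 70% (42% and 94% with residual variance 2).

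Fourth, a reader might infer that averaging biases the result whenever a visit is missed, despite the statement "So if there are missing outcome values in any phase due to participant dropout, the usual analysis will still be valid". The plan gives no rule for a phase with one visit missing. Section 9.1 requires baseline and week-6 BFI for a woman to be evaluable, and the plan does not say which set the phase model uses. No size can be given for such a bias.

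Finally, the exact match with half kept needs the full effect at week 12. Linear decay matches one third instead.

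**Conclusion.** The point holds in limited form. The analysis assigned to Aim 2 depends on weeks 12 and 24 only through their sum, so it cannot show how long the effect lasts. Under the power section's means, an effect lost by week 24 and one half kept throughout give identical phase means, 3.75 and 3.75, and an interaction of 0 between arms when the between-arm difference follows the same pattern. The loss of timing information does not rest on the variance reading or the sample size; only the power figures do. The decay courses are illustrations, not predictions.

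Aim 2 is exploratory, and the primary week-6 conclusion is not affected. The data and a suitable model are both in place, so this is a fault in which analysis is assigned to the aim and not in the design. Keeping the visits apart makes the courses distinguishable in principle, but a half-kept effect against sham would still be estimated imprecisely.

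**What to change.** For Aim 2, replace the phase-average model with the group-by-week model already planned for each outcome. Name the contrasts: relaxing minus sham and relaxing minus no treatment, at week 12 and at week 24 separately, each with a 95% interval. Base the duration conclusion on those two visits, with week 24 as the result for the longest follow-up.

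The cost is about a paragraph of SAP wording, with no new data and no new model. Each single-visit estimate has an SE about 15% larger than that of the two-visit average, which is acceptable for an exploratory aim whose question is timing.
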